1. RESUME

Principal Investigator name: [name] [name]		
STUDY TITLE: Randomized Clinical Trial to assess the safety and efficacy of a mobile application to accompany and empower patients undergoing bariatric surgery: the VAMOS project (Virtual Accompaniment for Morbid Obesity Surgery)		
STUDY TYPE: Randomized Clinical Trial		

INTRODUCTION:

Morbid obesity is considered the great epidemic of our century. It is regarded as the first non-traumatic cause of death in the western population and it is also progressively beginning to affect developing countries. The latest epidemiological studies estimate that in Spain more than 15% of the population has overweight and about 5% has morbid obesity.

Obesity treatment is multidisciplinary, from lifestyle and dietary changes to surgery. Amongst the different available treatments, bariatric surgery is the only cost-effective in patients with morbid obesity. Bariatric surgery provides better results compared to both pharmacological treatments (which are less available and less effective) and lifestyle changes. Furthermore, as well as weight loss, it guarantees a better control of comorbidities, reducing the risk of cardiovascular disease, morbidity and mortality, improving quality of life.

Although surgery is the best treatment option, patient commitment is necessary to achieve satisfactory results. Obtaining patient's comprehension of the importance of healthy lifestyle and equilibrated diet alongside with surgical information is generally difficult. Patient's concern needs to be constantly stressed out. The ongoing protocols that include preoperative meetings with surgeons, endocrinologists and nutritionists have been proved as insufficient, especially during the Covid-19 pandemic, when presental visits were reduced or cancelled.

Preoperative optimization with a healthy lifestyle and a balanced diet few months before surgery potentially reduce intraoperative complications alongside with postoperative morbidity and mortality [1-3]. Level of physical activity, diet and psychological stability could affect surgery's outcome for example reducing liver volume (up to 20%) and mesenteric fat [4-13]. Also, an improvement in patient's preoperative satisfaction, anxiety and commitment to surgery have been suggested [14-16]. Their impact on postoperative outcomes is unclear. There is lack of consensus on a standardized preoperative approach and goals. Many health care professionals worldwide strongly believe that preoperative optimization has an important impact on postoperative outcomes, but the evidence supporting this belief is mixed and most often retrospective. Although a positive relationship between self-monitoring behaviors (such as daily food intake diaries and regular self-weighing) and weight loss has been proved, additional instruction and behavioral intervention are needed. Besides weight loss, other factors such as adherence to self-monitoring of weight, recording food intake, increased physical activity could influence postoperative outcomes [17].

Even though official guidelines for an enhanced recovery (ERAS, Enhanced Recovery After Surgery) in bariatric surgery recommend patient information, education, counseling and preoperative weight loss, the efficacy of these measures has not been proved [18].

Technological development is an important resource that could help improving communications between patients and health care professionals. Nowadays, the use of a smartphone is widely integrated in daily life of most people [19,20]. The number of smartphones used is constantly increasing every year. In 2016, there were more than seven billion users worldwide [21]. The worldwide fast widespread of mobile technology in the last 15 years led to an expansion of the applications (APP) market [22]. To date, the biggest APP market are 'Google Play' (Android), 'App store' (Apple) and 'Blackberry World' (Blackberry) [23].

This technological revolution has progressively affected the health world. An increasing number of medical APP have been designed in the last years, few directly managed from health care providers from public or private centers. ThemHealth (Mobile Health) APP could led to a simpler, real-time connection between patients and health care professionals alongside with a bidirectional data flow and a steadily monitorization of patients' evolution that could obtain a better preoperative follow-up without increasing the costs [24-26].

The present randomized clinical trial aims to prove the safety and efficacy of an interactive mobile application (Care4Today®) to obtain sufficient weight loss and empower patients with morbid obesity before being submitted to a gastric by-pass.

HYPOTHESIS:

Main hypothesis: The preoperative use of the Care4Today (C4T) application in addition to standard protocol, in patients with a grade II-III obesity (BMI between 35 and 50 Kg/m²) achieves greater preoperative weight loss than standard protocols.

Secondary Hypothesis: Use of the Care4Today (C4T) application in the preoperative setting achieves:

- less intra- and post-operative complications at 30 and 90 days;
- less technical complexity and duration of surgery;
- better patients' information and satisfaction;
- better medical team coordination and satisfaction;
- better weight loss outcomes at mid-term (1, 3 and 5 years).

AIMS:

Main goal: To compare patients' preoperative weight loss after using the C4T APP in addition to standard protocol versus the standard preoperative protocol.

Secondary goals:

1. Compare patients' information / satisfaction using the APP vs. standard protocol.
2. Compare complications in the immediate postoperative period (30- and 90-days post-intervention) after the preoperative use of APP vs. standard protocol.
3. Compare medical team coordination / satisfaction using the APP vs. standard protocol.
4. Compare patients' weight loss 3 months after surgery using the APP vs. standard protocol.

STUDY DESIGN: Randomized Clinical Trial to assess the safety and efficacy of a mobile application to monitor patients undergoing bariatric surgery.

All patients will receive the standard preoperative protocol that consist in optimization of associated complications with an active management of obesity-related comorbidities, optimization of preoperative weight loss through a hypocaloric diet carried out during the 10-15 days prior to surgery and an informative and educational group session prior to surgery (EDUBAR). The C4T APP will be provided four months before surgery to all the patients randomized in the APP group. All the contents in the APP have been properly selected and modified by the multidisciplinary team (endocrinologist, pneumologist, anaesthesiologist, psychiatrist, nutritionist, nursery). Specifically, the APP contents include informative articles covering the nutritional, behavioral, and surgical fields, exercises, interactive charts, instructional videos, surgical animations, checklists, and frequently asked questions. The format of the APP will lead the patient through a virtual journey in the world of bariatric surgery, allowing to understand all the basic information about the preoperative period, the surgery and hospitalization and the postoperative follow-up. The use of the APP will influence preoperative weight loss through all the information provided, designed in an intuitive way so that the patient progresses in their level of knowledge and can assess through a checklist if they are doing the correct training. It will allow patients to set specific goals and assess their scope. Making patients aware of the importance of preoperative weight loss through training will be the key to obtaining correct adherence to the program and satisfactory preoperative weight loss. No patient data will be saved on the APP.

To assess the impact of the APP, in addition to standard protocol, in the pre- and postoperative period, we will compare:

- preoperative total weight loss percentage
- level of patient information
- level of patient satisfaction
- level of medical team satisfaction
- 30th and 90th days postoperative morbidity and mortality
- percentage of weight loss 3 months after surgery

CHRONOGRAM:

OBSERVATION PERIOD

Recruitment period of the study is expected to be 18 months, with additional 6 months to perform surgeries and follow-up. All information's will be obtained using the application flow of data alongside with presential meeting with surgeons, endocrinologists, nutritionists.

S. All the contents in the APP have been properly selected and modified by the multidisciplinary team. The day of surgery all the data about weight loss, patient and medical team satisfaction will be collected. Then, patients will be followed in observation of our standard postoperative protocol to assess the 30th and 90th postoperative morbidity and mortality alongside with weight loss evolution. The PhD student has been directly involved in the APP design and contents creation. He will perform the preoperative presential meeting to provide and explain the APP functioning to the patients in the APP group. Furthermore, he will collect the data on the day of surgery, during surgery and will be directly involved in postoperative follow-up of all patients.

STUDY POPULATION:

Inclusion criteria:

- Patients older than 18 and younger than 65 years who meet criteria to undergo bariatric surgery
- BMI between 35 and 50 kg/m² and indication of one-time surgery
- Signing the informed consent of the study
- Patient suitable for laparoscopic surgery
- Patient who demonstrates accessibility to a smartphone and basic digital competence (Appendix 1).

Exclusion criteria:

- Previous bariatric surgery
- Two-step surgery
- Patient without resources to access the use of a Smartphone or without basic digital competence
- Contraindication for surgery
- Other surgical procedures associated with the same intervention

Retirement criteria:

- None

EXPERIMENTAL TREATMENT: Use of a mobile application to accompany and empower patients in the preoperative period.

EVALUATION CRITERIA:

Main criteria (for the main goal): Preoperative percentage of excess weight lost (%EWL), considering ideal BMI = 25, will be recorded.

Following the follow-up protocol in General Surgery Outpatient Consultations, patients' weight will be measured 4 months before surgery and on the same day of surgery; then at 3, 6 and 12 months, and then every year up to 5 years of follow-up to calculate BMI and percentage of overweight lost, percentage of BMI lost, total weight and BMI lost.

Secondary criteria (for secondary goals):

1. Patients' information and satisfaction using the APP vs. standard protocol will be evaluated using approved questionnaire (appendix 2, appendix 3);
2. Morbidity and mortality: morbidity and mortality will be evaluated using the prospective database of the Bariatric Surgery Unit and the electronic medical record of each patient. All perioperative aspects related to the surgery will be reviewed. Complications will be recorded according to the Clavien-Dindo classification.
3. Metabolic comorbidities: Comorbidities related to metabolic syndrome and morbid obesity will be recorded to study their evolution up to 5 years after the intervention: DM2, hypertension, DL and OSAS.
4. Medical team coordination and satisfaction using the APP vs. standard protocol will be evaluated during multidisciplinary committee.
5. Patients weight loss 3 months after surgery will be evaluated using the prospective database of the Bariatric Surgery Unit and the electronic medical record of each patient.
6. Nutritional and metabolic deficiencies: The analytical studies performed each year on these patients will be evaluated to detect possible deficiencies: protein, iron, phosphocalcic, fat-soluble vitamins and trace elements.

STUDY DURATION:

The study is expected to begin in October 2022

Patient recruitment period is expected from October 2022 to March 2024.

Preoperative follow-up will be completed the day of surgery.

Mid-term follow-up (2 years) will be completed in March 2026.

Long-term follow-up (5 years) will be completed in March 2029.

SAMPLE SIZE:

The sample size was calculated in 142 patients divided into two groups of 71 patients each. It was calculated by comparing a hypothetical reduction of ≥ 5 kg in 55% of patients in the C4T group vs in 39% of patients in the control group [27] with a possible loss of 16% of patients, a confidence level of 95%, and statistical power of 80%.

STATISTICAL ANALYSIS:

Continuous variables will be expressed as mean \pm standard deviation or median (interquartile range) as appropriate. Differences between both techniques will be evaluated using a parametric test (χ^2 for categoric variables and t test for continuous variables). We'll use the IBM-SPSS Statistics Version 20 computer software to analyse all the statistics. A p value < 0.05 will be considered statistically significant.

PERSONAL DATA PROTECTION / CONFIDENTIALITY / ETHICAL ASPECTS:

This study may be developed in agreement with protocol and Good Clinical Practice (GCP) guidelines, like is described in Administration 91/507/EECC and Declaration of Helsinki, regarding the investigation with humans ("Ethical Principles for Medical Research Involving Human Subjects"). Researchers accept to follow these instructions and procedures described therein and therefore will comply with the principle of Good Clinical Practice on which it is based.

Informed consent.

A signed informed consent to participate in the study will be obtained (Appendix 4). Each patient will be informed about study nature and will receive an informative document about the study (Appendix 5). Patient will sign the informed consent for diagnostic and therapeutic procedures of the Hospital, as well as the specific consent to accept inclusion in the study.

CONFIDENTIALITY

Patients will be identified by a serial number and by the medical record number. Only study investigators will have access to this database. In any case, all the information (personal and clinical) collected from patients undergoing bariatric surgery will be treated in accordance with REGULATION (EU) 2016/679 OF THE EUROPEAN PARLIAMENT AND OF THE COUNCIL of April 27, 2016 regarding the protection of persons regarding the processing of personal data and the free circulation of these data, as well as the rest of the laws and regulations in force and applicable, such as Organic Law 3/2018, of December 5, on the Protection of Personal Data and guarantee of the rights digital.

ETHICAL ASPECTS

Approved with Approval number: Ref PR150/22 by the Comité de Ética en Investigación Clínica, of University Hospital of Bellvitge, [name], [contact], [name].

BENEFITS OF RESEARCH

To date, preoperative optimization has been considered as an important factor that influences the postoperative outcomes, but the evidence supporting this belief is mixed and most often retrospective.

Our research will provide a clear, high-level evidence about the importance of preoperative weight loss in obese patients to improve short- and long-term outcomes. Furthermore, we aim to demonstrate that technology could be an essential mean to improve patients' and medical team connections to obtain better treatment results.

BIBLIOGRAPHY:

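### The introduction sets out to prove the APP's safety, but the only safety-related analysis is a superiority test on complications with no margin, interval or safety criterion

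*Combined protocol and SAP*

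**What the plan says.** All references are to section 1 (Resume) of the combined protocol and SAP.

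- **Introduction, last paragraph:** the trial "aims to prove the safety and efficacy of an interactive mobile application". The study title and the Study Design line use the weaker verb *assess*.
- **Hypothesis:** the secondary hypothesis is directional. It expects "less intra- and post-operative complications at 30 and 90 days" with the APP.
- **Aims, secondary goal 2:** "Compare complications in the immediate postoperative period (30- and 90-days post-intervention) after the preoperative use of APP vs. standard protocol". No listed goal is labelled as a safety goal.
- **Study Design:** the list of comparisons includes "30th and 90th days postoperative morbidity and mortality". The APP is handed out four months before surgery.
- **Evaluation Criteria:** "Complications will be recorded according to the Clavien-Dindo classification". No grade threshold and no expected rate are given.
- **Statistical Analysis:** "Differences between both techniques will be evaluated using a parametric test", with chi-square for categorical variables, and "A p value < 0.05 will be considered statistically significant". No confidence interval for a difference is planned.
- **Sample Size:** 71 per arm, 16% loss. The calculation rests on weight loss alone.

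**The concern.** To show that an intervention is safe, a trial must put an upper bound on the harm it could cause. That takes an interval estimate and some statement of how much excess harm would be tolerated. This plan has neither. Its one tool for complications is a test of whether the arms differ, set up to look for benefit. If that test is not significant, the plan yields nothing that bears on safety, because the absence of a detected difference is compatible with a sizeable excess when events are few.

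The gap also runs in time. The APP is used before surgery, but the listed comparisons begin with the operation. Adverse events during the months of APP use, and patients who never reach surgery, enter no planned comparison. At stake is what the final report may say about safety, a word that stands in the study title.

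**Working it through.** **Inputs.** From the protocol: 71 per arm; 16% loss, so 71 × 0.84 = 59.6, about 60 evaluable; chi-square; p < 0.05 (sidedness not stated, two-sided taken). Not in the protocol: any complication rate. The rates below are assumptions, shown as a range.

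**The plan's own figure.** The only sizing figure is 71 per arm for 55% vs 39%. The two-sided pooled formula gives [1.96√(2 × 0.47 × 0.53) + 0.8416√(0.55 × 0.45 + 0.39 × 0.61)]² / 0.16² = 151.6, so 152 per arm, or 152/0.84 = 181 after loss. The stated 71 is not reproduced. That is a separate matter; here 71 and 60 are taken as the numbers the trial will have. No figure in the plan concerns complications.

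**1. Interval for the risk difference, equal observed counts (Newcombe).** With Wilson limits l and u around p, the half-width is √[(p − l)² + (u − p)²].
- 7/71 in each arm: p = 0.0986, l = 0.0486, u = 0.1898. Half-width √(0.0500² + 0.0912²) = 0.104, i.e. ±10.4 points.
- 6/60 in each arm: p = 0.1000, l = 0.0466, u = 0.2015. Half-width √(0.0534² + 0.1015²) = 0.115, i.e. ±11.5 points.

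**2. Power to detect a true doubling.** Exact binomial enumeration of the uncorrected chi-square, counting rejections in the direction of harm:

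| Assumed rates | 60 per arm | 71 per arm |
|---|---|---|
| 5% → 10% | 17.3% | 20.6% |
| 10% → 20% | 32.6% | 38.8% |
| 15% → 30% | 51.4% | 58.5% |
| 20% → 40% | 68.4% | 75.5% |
| 25% → 50% | 81.8% | 87.6% |

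**3. When is a doubling excluded?** With x events of n in each arm, the 95% limits for the risk ratio are exp[±1.96√(2/x − 2/n)].
- 4/71: 0.26 to 3.84
- 7/71: 0.37 to 2.70
- 11/71: 0.46 to 2.16
- 14/71: 0.51 to 1.94
- 18/71: 0.57 to 1.76
- 12/60: 0.49 to 2.05
- 13/60: 0.51 to 1.97

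The upper limit first drops below 2 at 14/71 (20%; 13/71, 18%, by the score method) or at 13/60 (22%).

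**4. A non-significant result that is not reassuring.** With 9/71 vs 18/71 the chi-square gives p = 0.054. The Newcombe interval for the excess of 12.7 points runs from −0.3 to +25.3 points. The p-value alone hides this; the interval shows it.

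**5. Deaths.** Zero deaths in 71 leaves an upper limit of 1 − 0.05^(1/71) = 4.1% (one-sided 95%) or 1 − 0.025^(1/71) = 5.1% (two-sided).

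**The case against.** The best reply is that this turns on one verb. *Prove* is used for this aim only in the closing paragraph of the introduction; the title and study design say *assess*, and the Aims list promises only to compare complications. The intervention is educational content added to standard care that every patient receives, and complications are a secondary comparison. All of that is correct, and it limits the weight of the point. It does not remove the point, because even assessing safety needs an estimate with its uncertainty, and none is planned.

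Two stronger readings are tempting, and the documents do not support either.

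- A reader might infer that the plan treats p ≥ 0.05 as proof of safety. No section says so. The written hypothesis is fewer complications, so a non-significant result is formally a failed superiority hypothesis. What can be said is that such a result could not support the introduction's aim, and that the plan does not say how it would be interpreted.
- A reader might infer that a trial of this size can never exclude a doubling. That depends on a rate the protocol does not give. With equal observed rates of about 20–22% or more, a doubling is excluded, and at 25% the power to detect one exceeds 80%. Because no Clavien-Dindo threshold is set, the any-grade rate could lie on either side of that line.

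On the preoperative gap, it can be argued that the hypothesis also covers intraoperative events and that perioperative aspects of the surgery will be reviewed. Neither clearly reaches the four months of APP use. A cancelled operation is also partly a retention matter rather than a harm, which is a reason to list it separately instead of counting it as a complication.

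**Conclusion.** The point holds as a mismatch between one stated aim and the planned analysis. The mismatch itself does not depend on any assumed rate: a superiority test with no margin, interval or criterion cannot prove safety.

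Its size does depend on assumed rates. At 10% per arm the uncertainty is roughly ±10 to ±12 percentage points, and a true doubling would be missed about two times in three (power 33–39%). From 5% the power is 17–21%, and from 15% it is 51–59%. Below about 20% with equal observed rates, a doubling stays inside the 95% interval; above about 22% it does not. These figures assume 60 to 71 evaluable patients per arm and a two-sided 5% level. The consequence is limited to what may be concluded about safety; the primary weight-loss comparison is not affected.

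**What to change.** 1. In the introduction, replace the aim of proving safety with *assess* (matching the title) or *describe*.
2. Alongside the chi-square test, report 30- and 90-day postoperative complications by Clavien-Dindo grade, and deaths, as counts per arm and risk differences with 95% confidence intervals.
3. List separately, by randomised arm, adverse events and failure to reach surgery between randomisation and the operation. Keep the 30- and 90-day windows anchored at surgery: with the APP given four months earlier, windows started at randomisation would close before the operation.
4. State that any safety conclusion will be drawn from the intervals and not from p ≥ 0.05.

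The cost is a more modest safety claim and a little more recording and analysis; no extra patients are needed. If the sponsor wishes to keep the stronger aim, a justified margin and a trial sized for it would be required. For scale, ruling out a doubling of an assumed 10% rate when the true rates are equal (one-sided 0.025, 80% power) needs (1.96 + 0.8416)² × 2 × 0.1 × 0.9 / 0.1² = 141.3, so 142 evaluable per arm, or 142/0.84 = 170 per arm after 16% loss.

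### The trial claims to assess the safety of an APP used before surgery, but its planned comparison of complications and deaths runs only from surgery onward

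*Combined protocol and SAP*

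**What the plan says.** All references are to the Combined protocol and SAP, section 1 (Resume).

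- **Safety is a declared purpose.** It is in the title and the study design line, and the introduction closes with "The present randomized clinical trial aims to prove the safety and efficacy of an interactive mobile application (Care4Today".
- **The intervention is preoperative.** Under Study Design: "The C4T APP will be provided four months before surgery to all the patients randomized in the APP group". Under Experimental Treatment: "Use of a mobile application to accompany and empower patients in the preoperative period". Background care is common to both arms: "All patients will receive the standard preoperative protocol".
- **The safety comparison is tied to the operation.** The secondary hypothesis expects "less intra- and post-operative complications at 30 and 90 days". Secondary goal 2 is "Compare complications in the immediate postoperative period (30- and 90-days post-intervention) after the preoperative use of APP vs. standard protocol". The list of items to be compared, under Study Design, has "30th and 90th days postoperative morbidity and mortality".
- **Data collection follows the same order.** The observation-period text has weight loss and satisfaction collected on the day of surgery, with follow-up for morbidity and mortality coming after that.
- **Secondary criterion 2** takes morbidity and mortality from the unit's prospective database and each patient's electronic medical record, reviews the perioperative course of the operation, and grades complications by Clavien-Dindo. It states no start date.

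**The concern.** The period in which the intervention is defined to act and the period in which harm is counted do not overlap. The plan introduces its list of comparisons as covering the APP's impact both before and after surgery. The preoperative items on that list are weight loss, information and satisfaction; none is a safety item.

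Two things follow. First, a death, an unplanned admission, an emergency visit or an operation cancelled for medical reasons during the APP months is not planned to be reported by arm. Second, postoperative complications exist only for patients who were operated on, so anyone who dies, falls ill or withdraws before surgery leaves the safety comparison altogether. A report that followed the plan exactly could make a statement about APP safety with no planned data from the months of defined use, and on a subset selected after randomisation.

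**Working it through.** **1. Planned windows side by side**

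| Place in section 1 | What is counted | When |
|---|---|---|
| Secondary hypothesis | Complications | During surgery, 30 and 90 days |
| Secondary goal 2 | Complications | 30 and 90 days after surgery |
| List of comparisons (Study Design) | Morbidity, mortality | 30 and 90 days after surgery |
| Observation period | Morbidity, mortality | After the day of surgery, 30 and 90 days |
| Secondary criterion 2 | Morbidity, mortality | Perioperative, start not given |
| Main criterion | Weight | Four months before, and day of, surgery |

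Within the APP months the only study measurements scheduled are the starting weight and the day-of-surgery weight, with satisfaction added on the day of surgery. There is no definition of an adverse event and no rule for recording why a patient did not reach surgery.

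**2. Calendar time.** Taking four months as about 120 days:

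120 / (120 + 90) = 120 / 210 = 57% of the time from APP provision to postoperative day 90 has no planned safety count.

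**3. Possible number of events.** The documents give no preoperative event rate, so a range is assumed. The sample size of 142 (71 per arm) is taken as stated.

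| Assumed rate | Both arms (× 142) | Per arm if rates are equal (× 71) |
|---|---|---|
| 2% | 2.8 | 1.4 |
| 5% | 7.1 | 3.6 |
| 10% | 14.2 | 7.1 |

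**4. What such counts could show.** If no event is seen in n patients, the one-sided 95% upper limit for the event rate is 1 − 0.05^(1/n).

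- n = 71: 1 − 0.05^(1/71) = 4.1%.
- n = 60 (71 × 0.84 = 59.6, after the 16% loss the plan allows): 1 − 0.05^(1/60) = 4.9%.

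The chance of seeing at least one event among 71 patients is 1 − (1 − p)^71: 51% for p = 1%, 76% for p = 2%, 97% for p = 5%. The counts can describe, and can exclude only fairly common harm. They cannot support a formal comparison.

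**5. Effect on the postoperative comparison.** In one arm of n patients let k not reach surgery. Let r be the complication rate in those operated on, and s the rate that the k patients would have had if operated on. The rate in all n would be [(n − k)r + ks]/n, so

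observed − full = r − [(n − k)r + ks]/n = (k/n)(r − s).

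The sign depends on whether r or s is larger, and the size cannot exceed k/n. The documents give none of k, r or s. The sample size text allows for 16% loss, 0.16 × 142 = 22.7 or about 23 patients, but does not say when or why they would be lost.

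**The case against.** The strongest reply has four parts.

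- **Criterion 2 is open-ended.** It gives no start date, it uses the medical record, and the perioperative period can include some time before the operation. That is fair as far as it goes. But the goal it serves is dated from surgery, as are the list of comparisons and the follow-up description, and nothing extends the review back four months. Finding an event incidentally in the record is not a planned comparison by arm.
- **Patients are not out of sight.** Both arms receive active care of comorbidities, and information comes from in-person meetings with surgeons, endocrinologists and nutritionists. This stands: a reader might infer that patients are clinically unobserved for four months, and the documents do not support that. What is missing is the planned tabulation. The APP does not supply it, because it stores no patient data and controls do not have it.
- **The APP is informational and probably low-risk.** The documents describe articles, videos, checklists and goal-setting. The hypocaloric diet before surgery is given to both arms and falls inside the four months, so it is not a difference between arms. This limits the importance of the point. It does not remove it, because the plan itself claims to prove safety.
- **Postoperative complications are a legitimate outcome of the APP.** Agreed. The safety assessment is incomplete, not irrelevant.

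A reader might also take the APP months as the only time when the arms differ. The defined treatment is preoperative, but the document does not say that access ends at surgery, and the APP content extends to postoperative follow-up.

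**Conclusion.** The point holds in a limited form. Safety is claimed for an APP whose defined use is preoperative, while the planned comparison of complications and deaths runs from surgery onward (intraoperative, 30 and 90 days). No preoperative event is planned to be counted by arm, and patients who never reach surgery drop out of the safety comparison.

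The 57% rests on reading four months as 120 days and measures calendar time, not risk. The 3, 7 or 14 untabulated events rest on assumed rates and pool both arms.

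Two stronger readings are tempting and not supported:

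- *That preoperative harm would make the APP arm look safer.* A patient who misses surgery leaves both numerator and denominator. By the expression (k/n)(r − s), the observed rate may move either way, so the direction is unknown.
- *That the plan ignores a nutritional risk of preoperative weight loss.* Secondary criterion 6 says "The analytical studies performed each year on these patients will be evaluated to detect possible deficiencies", but it does not link those deficiencies to preoperative weight loss. It is a separate follow-up outcome and forms no part of this point.

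This is an inexpensive improvement that should be made. It does not affect the primary comparison of preoperative weight loss.

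**What to change.** Amend secondary goal 2 and secondary criterion 2 as follows.

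1. Count events in all randomised patients of both arms, from randomisation to 90 days after surgery. The document does not say how randomisation is timed relative to APP provision. If the two dates differ, use the weight visit four months before surgery as the common index date, since both arms have it.
2. Extract from the electronic medical record already named: deaths, unplanned admissions, emergency visits, and cancelled or postponed surgery with the reason.
3. State where counting ends for a patient who is never operated on. One workable choice is 210 days from the index date, the planned 120 + 90.
4. Report the preoperative period and the 30- and 90-day postoperative periods separately, by arm, as counts and proportions without a formal test. Show how many patients in each arm reached surgery.

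If this is not done, restrict the safety conclusion to perioperative outcomes in operated patients.

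The cost is a wording change and a longer chart-review window in a record already under review. Contacts outside the hospital may be missed, since the document does not describe the record's coverage; that limitation should be stated in the report. A few events unfavourable to the APP may also appear.
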